Title: The Effects of Repetitive Transcranial Magnetic Stimulation Prefrontal Target Location on
Outcomes for Major Depressive Disorder

ID: 201709834

Date: 08/22/2019

Study Procedure Timeline and Protocol

Eligible patients will be identified during clinical transcranial magnetic stimulation intakes, which occur weekly in the psychiatry clinic (2JPP clinic). Interviews are conducted by physicians who are members of the research team. If a patient is identified as eligible for the study, he or she will be asked if they are interested in participating in the research study. If they answer yes, a study physician will set aside time at the end of the appointment to discuss the details, or will obtain information and permission to contact the patient over the phone after the appointment to provide details.

After detailed description of the study, if patient is willing to participate and meets study criteria, consent form will be signed. This will occur on the day the patient presents for initial testing as part of the research study. Once expressing interest, the patient will work with the study physician or a research team member to set up a date and time for the patient to come in for cognitive, psychological, and neurobehavioral testing, and, in a subset of patients, an MRI scan. If they choose not to participate, they will proceed with rTMS treatments as is standard clinical care.

Participants who are interested in the study will present for their baseline testing prior to initiation of their rTMS treatment course. The testing will occur in a designated research space, likely W264 or T212 in General Hospital. This is estimated to take 1-3 hours, depending on whether or not an MRI is included. These assessments include NIH Toolbox cognitive and emotional batteries (30-45 minutes), Temperament and Character Inventory (30 minutes), MOCA, CGI, PHQ-9 and MADRS (20-30 minutes total), and neurobehavioral testing and neurologic exam (30-60 minutes). Patients will have heart rate variability and facial movements monitored while viewing video clips or images, or hearing stories that may be emotionally charged or neutral (10-15 minutes). EEG will be recorded at rest and during tasks (30 minutes). Some patients may be given an actigraphy wristband to monitor their daily level of activity and their circadian rhythms. Some of these assessments are already obtained as part of the initial work-up for rTMS patients and that data is available for review under a separate previously approved IRB. The neuroimaging will include 21 minutes of resting state fMRI, T1rho, T1 MPRAGE, and DTI (<=60 minutes total). A research team member will escort the patients receiving MRIs to the MRI scanner and back. If a subject chooses to participate in the Vocal Pattern detection portion of the study, they will complete the procedures once weekly for the entirety of their TMS treatment course. The research team member will schedule this with the subject in advance so they are prepared for the length of the visit. Subjects will complete the PHQ9 questionnaire, if they have not already. Next, the recording part will begin with the reading the Grandfather Passage, and the Rainbow Passage. Finally, the subject will be asked some questions about your daily life and your interests.

The course of TMS will occur as clinically determined by the TMS physicians providing the patient's care. The only unique aspect is that patients in the study will be randomized to either receive rTMS at the F3 location (determined using free software from clinicalresearcher.org) or the 5.5cm method, as is the current standard of clinical care at the University of Iowa for clinical rTMS treatments. Some early internal data has shown that these targets can vary anywhere from a few millimeters apart to a few centimeters, but all targets are within the prefrontal cortex on the left side and consistent with the FDA-approved treatment region for major depressive disorder. The nature of these targeting strategies

should prevent any target from ever falling outside a clinically approved range, but if for some reason it appears that a target is outside of the FDA-approved target region, a study physician will be called to evaluate and confirm the targeting, and adjust if felt to be clinically inappropriate (e.g., not in the prefrontal cortex for that patient). Noninvasive autonomic measures will be obtained during the course of treatment including blood pressure, heart rate, pupil size, and facial movements, although this should not interfere with or delay the administration of the TMS therapy. Some of these measures are already intermittently obtained on patients undergoing TMS therapy.

Treatment will then proceed as managed by the clinical rTMS service at University of Iowa. Follow-up appointments will occur as clinically scheduled by the rTMS clinical service and the patient's other providers as is standard of care. The patient and raters will be blinded to the treatment target for each patient, which will be assigned randomly. The treatment technician will be aware of the treatment site as needed for performing the appropriate measurements and targeting procedure during appointments.

After a patient has either completed their rTMS course or the course has been terminated by the rTMS team for whatever reason, the patient will have the same testing performed as was performed at their initial study visit. This may include an MRI if patient consented to this and a pre-treatment MRI was conducted on the patient. For purposes of the study, the follow-up MRI could occur either at the very end of the treatment course or at some point during the treatment course, as determined by the study physicians and with patient approval/agreement. They will then be asked to schedule a follow-up phone call 4-6 weeks after completion of the rTMS treatment course, and some questionnaires may be administered over the phone at that time, including a PHQ-9. After this visit, they will no longer be a part of the study.

Recruitment

Patients will be recruited as described above. Only patients who come for and complete a clinical rTMS intake will be asked to participate in the study.

Determination of Treatment-Resistant Depression

Treatment resistant depression will be identified based on clinical interview by a physician with special training in rTMS or psychiatry. This will be a standard clinical interview that will confirm the diagnosis of major depressive disorder, rule out other causes of depression, and evaluate for previous failure of medication and psychotherapy trials. This is standard of care for rTMS treatment as determination of whether it is indicated for use for major depressive disorder, and thus occurs as part of every rTMS evaluation. After this appointment, further questioning may occur by the research study team if needed to confirm that patient meets study criteria or to clarify any information obtained during the clinical interview.

Inclusion Criteria

As per the IRB:

Inclusion:

- Diagnosis of major depressive disorder
- Age greater than or equal to 18 years
- Able to consent for treatment and research participation
- English-speaking
- Have been evaluated by a psychiatrist or neurologist with expertise in TMS and felt to be an appropriate candidate to undergo TMS treatments

Exclusion Criteria

As per the IRB:

Exclusion:

- Age less than 18 years
- Patients that are excluded during TMS assessment including:
- Patients with epilepsy or seizure disorder
- Patients with implanted ferromagnetic equipment in their face or skull near the stimulation target

MRI Exclusion criteria:

- Implanted device including pacemaker, coronary stent, defibrillator, or neurostimulation device that is not MRI-compatible
- Metal in body including bullets, shrapnel, metal slivers
- Claustrophobia
- Uncontrolled high blood pressure
- History of atrial fibrillation
- History of significant heart disease
- Hemodynamic instability
- History of kidney disease
- Pregnant

MRI

The MRI scan will occur as described in the study protocol. Only a small subset of all patients enrolled in the study will receive an MRI scan before and after the treatment course. These scans will be scheduled to coincide with the other parts of the study evaluation if possible. Patients who are asked to participate in the MRI portion of the study can choose to refuse to participate in the MRI portion and still participate in the other portions of the study, or can refuse all portions and receive rTMS as is the clinical standard of care. In a small subset of patients (n=25 approximately), a repeat neuroimaging or neurobehavioral assessment session may be completed partway through the TMS course to look for biomarker or imaging changes during the course of TMS. This will be arranged with the patient several days ahead of time with their consent, and they will have the option to decline to participate. If subjects take part in this MRI midway through treatment subjects will undergo a single session of TMS in a research area in close proximity to the research MRI scanners. We will be using the same protocol and parameters as the patients' clinically determined TMS sessions, and the same device (albeit a replica device purchased for research purposes). The purpose of this MRI and single session occurring in close

proximity to the scanners will be to allow for rapid post-treatment MRI to detect short-term function and metabolic brain changes.

Scales/Testing

All of the scales and testing involved in the study are as described above. The neurobehavioral testing that is discussed above is composed primarily of neuropsychological testing and emotional scales, as well as a neurologic exam (some portions of this, again, are already conducted as part of the standard work-up for the rTMS clinical service).

Targeting

Targeting either the F3 left prefrontal cortex location or the 5.5cm target location will occur as described above. Targeting the F3 location requires taking measurements of the head circumference, tragus-to-tragus distance, and nasion-to-inion distance, and using computer software to calculate the correct prefrontal target using head landmarks. The 5.5cm target location is determined by measuring 5.5cm anterior to the primary motor cortex of the brain, which is identified using a TMS procedure called motor threshold testing, all of which is done as part of the standard of care in clinical rTMS and will not be altered for this study. Targets will be marked onto a swim cap which the patient will wear during treatments, to ensure that the same target can be stimulated from treatment-to-treatment reliably, again, as is standard practice in rTMS treatments.

Treatment as Usual (Parameters)

Treatment parameters other than stimulation location will be as per clinical standard of care, including 3000 total pulses at a frequency of 10Hz, with 4-second train duration, 26-second off time, for 75 total trains. All treatments will be targeted at the left prefrontal cortex as is FDA-approved for major depressive disorder, and all treatment targets will fall within this region.

Safety

All treatments will follow the standard of care safety procedures for clinical rTMS. An rTMS-trained technician will be present with each patient during the entirety of their treatment, with a study physician immediately available if needed for emergent response (such as for induced seizure). There is no evidence to suggest the risk of seizure is higher with stimulation at either target being investigated in this study. Management of seizure will occur as is standard practice for clinical rTMS. If a patient were to indicate suicidal thoughts during the course of their work-up and evaluation for this study, it would be managed as per standard of care for the clinical rTMS service, which involves a thorough safety risk assessment by a team physician, appropriate safety planning, and transfer to a higher level of care as clinically indicated. This may involve anything from providing additional resources for crisis intervention, discussion with the patient's primary psychiatrist or family (if patient provides consent to do so), or transfer to an emergency room for further evaluation. As a study physician will be either conducting all portions of the study evaluation or immediately available, and all study physicians

involved are also involved in standard clinical rTMS care, this should not be onerous and should be well within the scope of the team's clinical abilities.

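### Patients are to be blinded to the target, but the two set-ups as written may be distinguishable; measuring both targets in every patient before allocation is opened would be a cheap protection

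*Protocol*

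**What the plan says.** The blinding statement is in the Protocol, under Study Procedure Timeline and Protocol: "The patient and raters will be blinded to the treatment target for each patient, which will be assigned randomly". The technician is exempt from blinding and knows the site in order to make the measurements that suit it.

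The Protocol's Targeting section describes the set-ups. For one arm: "Targeting the F3 location requires taking measurements of the head circumference, tragus-to-tragus distance, and nasion-to-inion distance", followed by "using computer software to calculate the correct prefrontal target using head landmarks". For the other: "The 5.5cm target location is determined by measuring 5.5cm anterior to the primary motor cortex of the brain". The motor site is found by motor threshold testing, and the sentence ends: "all of which is done as part of the standard of care in clinical rTMS and will not be altered for this study". In both arms, "Targets will be marked onto a swim cap which the patient will wear during treatments".

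Two further statements in the timeline section bear on the point. One arm uses "the 5.5cm method, as is the current standard of clinical care" at the site. On the distance between targets: "Some early internal data has shown that these targets can vary anywhere from a few millimeters apart to a few centimeters".

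PHQ-9, MADRS and CGI are taken before treatment and repeated after it, and a PHQ-9 may be taken by telephone 4 to 6 weeks later. The SAP compares mean changes and the rates of response and remission.

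**The concern.** Blinding the patient to a target works only if the patient cannot tell from the procedure which target was chosen. As described, one arm involves three tape measurements of the head and a computer calculation, and the other does not. A patient who has learned how the two methods work could use that difference.

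The outcomes make this worth attention. The patient completes the PHQ-9, and the MADRS and CGI depend on what the patient reports and on judgement. If patients inferred their arm and expected more from one method, the comparison of changes and of response and remission rates could shift. The planned analysis could not separate that shift from an effect of the target. A larger sample would reduce random error but not this kind of bias.

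**Working it through.** The plan gives no figure for blinding, so there is nothing to reproduce. The check sets the relevant statements side by side.

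1. **Which set-up steps are common to both arms?** Motor threshold testing is described as unaltered standard care, so it is probably done in every patient. That wording can also be read to cover the 5.5 cm measurement itself.

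2. **Which steps are tied to one arm?** The two readings of that sentence give:

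| Step | Narrow reading (only motor threshold testing is common) | Wide reading (5.5 cm measurement is also common) |
|---|---|---|
| Motor threshold testing | both arms | both arms |
| 5.5 cm measurement | 5.5 cm arm | both arms |
| Three head measurements | F3 arm | F3 arm |
| Software calculation | F3 arm | F3 arm |

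On either reading, the head measurements and the software run are described for F3 only. The technician's exemption points the same way, since it presupposes that the measurements depend on the assigned site.

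3. **Does any text equalise the set-ups?** No. Neither document says that both sets are taken in every patient or mentions a dummy measurement, a script for the technician or a check of blinding. Neither says when allocation is opened relative to the measurements.

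4. **What else would be needed for bias?** Three further links:
   - The patient must know which procedure belongs to which arm. This depends on what patients are told, which cannot be seen here.
   - The patient must expect more from one method. The documents do not describe expectations. The protocol calls one method the current standard, but nothing shows that patients hear this or which way it would move them.
   - The expectation must change the ratings. The documents give no figure for this.

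The text therefore supports a distinguishable set-up. It leaves each of the three later links open, so no size or direction can be calculated.

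5. **Is the remedy feasible from the plan's own description?** The protocol calls the F3 software free, and the motor site is already located as standard care. The added work is three measurements and one software run in the 5.5 cm arm and, on the narrow reading, one 5.5 cm measurement in the F3 arm. The 5.5 cm point needs the motor site, so allocation would have to be opened after motor threshold testing.

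**The case against.** The strongest reply is that this argues from silence. The protocol states that patients are blinded, and nothing in the Targeting section contradicts it. That section says how each target is calculated, not what the patient notices or is told. Each patient experiences one set-up and has no comparator. Both arms receive active left prefrontal stimulation with the same pulse parameters, and the targets may be only millimetres apart, so neither sensation nor the position of the mark clearly reveals the arm. The site may already measure everyone in the same way without having written it down.

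Most of this stands. It rules out the stronger readings a reader might infer:

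- **That the blind is broken or the text contradicts itself.** The documents show a difference in procedure, not that any patient recognises it.
- **That the bias favours one arm.** The label of current standard care does not establish what patients expect.
- **That its size can be judged against the SAP's planned 31% versus 35% remission.** That 4-point gap describes a hoped-for treatment difference. It says nothing about how far expectation might move ratings.
- **That raters are left unprotected.** The protocol already requires raters to be blinded to the target, which excludes anyone who knows a patient's target from rating that patient.

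The remedy can also be challenged: a patient who undergoes both procedures might see which one leads to the cap mark. That is a fair warning, and it is why the mark should be made out of the patient's view.

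The reply does not remove the central point. The written procedure ties a noticeable step to one arm, and the plan states no measure to equalise it.

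**Conclusion.** The point holds as an optional, low-cost improvement. As written, the set-ups may be distinguishable to a patient who knows the methods, and patient blinding rests on a statement with no procedure behind it. No unblinding is shown, and the size and direction of any bias in PHQ-9, MADRS or CGI cannot be quantified from the documents.

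The conclusion assumes that the Targeting section describes what is done, so that the head measurements and software run are confined to the F3 arm. If both sets are already taken in every patient, the sponsor need only say so.

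**What to change.** In the Protocol's Targeting section, state that in every patient, after the motor site has been located and before allocation is opened, the technician:

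- takes the three head measurements and runs the F3 software;
- measures the 5.5 cm point;
- records both targets and the distance between them;
- then opens the allocation and marks only the assigned target on the cap, out of the patient's view.

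This makes the set-up the same in both arms and keeps the measurements independent of allocation. It also gives each patient's distance between targets, for which the protocol now offers only a broad range from early internal data.

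The cost is a small amount of technician time per patient. That is an assumption, because the documents give no staffing or timing. Treatment, allocation ratio and sample size do not change. The patient still wears a marked cap and is treated by a technician who knows the target, so the risk is reduced, not removed.

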Title: The Effects of Repetitive Transcranial Magnetic Stimulation Prefrontal Target Location on  
Outcomes for Major Depressive Disorder

ID: 201709834

Date: 08/22/2019

rTMS Clinical Database (IRB ID#201709834)  
Data Analysis Plan

We will compare pre- and post-treatment rating scales, cognitive scores, and EEG/MRI results. Rating scales and cognitive/neurobehavioral scores will be analyzed using hypothesis-driven t-tests. iPad cognitive testing is normed to a US population adult control and results will be analyzed as T-statistics comparing the patients against a general population sample. A comparison of mean changes with confidence intervals and standard deviation calculations will be analyzed, as well as the difference in remission and response rates to treatment. For MRI we will compare structural volumetric changes, functional connectivity changes, T1rho pH changes, and DTI anisotropy changes.

Analysis pipeline is well established as mentioned above, with R package RnBeads and Minfi. We will control for standard demographics, including age, sex, race and psychotropic medication use known to affect DNA methylation status.

Audio recordings and their transcription are analyzed using a machine-learning algorithm to evaluate the predictive quality of vocal pattern detection and content value for treatment response to TMS.

Data received from IRB#201810778 will be used a comparison group for this study's heart rate variability data. Mean differences will be compared with t test statistics.

Based on previous work showing small efficacy differences between targets (31% remission with 5cm rule vs. 35% remission with certain Brodmann area targeting), power analysis with desired power of 0.80 and alpha of 0.05, we would need approximately 88 patients (44 in each group). We propose to recruit 200 patients.

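### The F3 versus 5.5cm comparison of the continuous rating scales is not adjusted for baseline, although the baseline scores are collected; ANCOVA would be a free gain in precision

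*SAP*

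**What the plan says.** The protocol's Study Procedure section sets up a randomised contrast: "patients in the study will be randomized to either receive rTMS at the F3 location" or by the 5.5cm method. The same section schedules PHQ-9 and MADRS, among other tests, before the course starts. The same testing is repeated once the course is completed or terminated.

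The first paragraph of the SAP opens with "We will compare pre- and post-treatment rating scales, cognitive scores, and EEG/MRI results". It then says "Rating scales and cognitive/neurobehavioral scores will be analyzed using hypothesis-driven t-tests", and later "A comparison of mean changes with confidence intervals and standard deviation calculations will be analyzed". The sentence on mean changes closes by promising a contrast of remission and response as well. None of these sentences names F3 or 5.5cm, and none names a baseline covariate or a regression model.

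The only covariate sentence is in the second paragraph and belongs to the methylation work: "We will control for standard demographics, including age, sex, race and psychotropic medication use known to affect DNA methylation status". It does not list baseline severity.

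The iPad cognitive scores have their own analysis, in which "results will be analyzed as T-statistics comparing the patients against a general population sample". They are outside this point.

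**The concern.** In a randomised trial that measures a continuous scale before and after treatment, the baseline score is usually the strongest available predictor of the final score. A t-test on change uses it only by subtraction, which fixes its coefficient at 1. ANCOVA estimates that coefficient from the data. If the true slope differs from 1, the change-score interval for the target difference is wider than the collected data allow.

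What is at stake is precision on MADRS, PHQ-9 and any other continuous scale on which the targets are to be compared. The SAP itself expects small differences between targets, so precision given up has some price. Chance imbalance at baseline is already part of the variance discussed here and should not be counted as a second harm.

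**Working it through.** **Inputs.** From the documents: two randomised arms; the same scales before and after the course; t-tests and mean changes with no covariate; a plan to recruit 200. Assumed: r = 0.3, 0.5, 0.7 (pre-post correlation within arm); k = 0.75, 1, 1.25, 1.5 (post-treatment SD divided by baseline SD); equal within-arm variances; for power, 1:1 allocation of the 200 (100 per arm, suggested by the equal groups in the SAP's last paragraph), complete pre/post data and two-sided alpha 0.05. The SAP gives no figure of its own for the continuous scales, so there is none to reproduce.

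**Formulas**, in units of the baseline variance:

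- Change score: V_change = 1 + k² − 2rk
- ANCOVA: V_ANCOVA = k²(1 − r²)
- Difference: V_change − V_ANCOVA = (1 − rk)²

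The difference is a square, so in large samples ANCOVA is never worse, and the two tie only when rk = 1.

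**Example**, k = 1.25 and r = 0.5: V_change = 1 + 1.5625 − 1.25 = 1.3125. V_ANCOVA = 1.5625 × 0.75 = 1.1719. The ratio is 0.893, a variance reduction of 10.7%. Interval width falls by 1 − √0.893 = 5.5%.

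**Variance ratio, ANCOVA to change score, with the reduction in interval width in brackets:**

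| k | r = 0.3 | r = 0.5 | r = 0.7 |
|---|---|---|---|
| 0.75 | 0.460 (32%) | 0.519 (28%) | 0.560 (25%) |
| 1 | 0.650 (19%) | 0.750 (13%) | 0.850 (8%) |
| 1.25 | 0.784 (11%) | 0.893 (5.5%) | 0.981 (1%) |
| 1.5 | 0.871 (7%) | 0.964 (2%) | 0.998 (0.1%) |

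**Finite samples.** A bivariate normal simulation with 20,000 replicates gave the mean ratio of interval widths. At k = 1 and r = 0.3/0.5/0.7 it was 0.808/0.869/0.925 with 100 per arm, 0.809/0.869/0.925 with 80 per arm (20% lost at random, assumed) and 0.811/0.872/0.927 with 44 per arm. These agree with the square roots of the ratios above. At k = 1.5 and r = 0.7 the ratio was 1.001 with 100 per arm and 1.005 with 44 per arm, so there ANCOVA gains nothing and pays a trivial price for the extra parameter. Bias from missing data was not examined.

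**Power.** With 100 per arm, the change-score t-test has 80% power for a difference of 0.398 SD of change (noncentral t, 198 df). For ANCOVA the degrees of freedom are 197 and the variance is inflated by 1 + 1/(2n − 4) = 1 + 1/196. Its power for the same difference is:

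| k | r = 0.3 | r = 0.5 | r = 0.7 |
|---|---|---|---|
| 1 | 93% | 90% | 86% |
| 1.25 | 88% | 84% | 81% |
| 1.5 | 85% | 81% | 80% |

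These figures are relative. They start from an effect chosen to give the t-test 80% power, not from an effect that the documents posit.

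**The case against.** A reader might infer more: that the t-tests are purely within-patient, so that the SAP contains no test or interval for the target effect on the continuous scales. The opening sentence, "We will compare pre- and post-treatment rating scales, cognitive scores, and EEG/MRI results", makes that tempting. The rest of the SAP does not support it. Comparing mean changes needs at least two sets of changes. The same sentence goes on to "as well as the difference in remission and response rates to treatment", and remission and response are states after treatment, so a difference in them implies groups. The last paragraph discusses efficacy differences between targets and says "we would need approximately 88 patients (44 in each group). We propose to recruit 200 patients". An unadjusted between-arm comparison of mean change is therefore the natural reading, and the missing arm names are loose wording rather than a missing analysis.

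A second overreading is that the t-test is biased or ignores baseline. It does neither: randomisation makes it valid, and a change score uses the baseline by subtraction.

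The strongest objection to what remains is that this is a choice of estimator with a gain of unknown size. The documents supply neither r nor k, the gain can be nil, and the only outcome that the SAP powers is remission, which is untouched. All of that stands. It limits the weight of the point but does not remove it: no baseline covariate is named for these scales, the data are already planned, and away from rk = 1 the gain is real.

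**Conclusion.** The point holds as an improvement in precision, not as the correction of an invalid analysis. For r from 0.3 to 0.7 and k from 1 to 1.5, ANCOVA would lower the variance of the F3 versus 5.5cm contrast by about 0% to 35% and the interval width by about 0% to 19%. With k = 0.75 the variance reduction is 44% to 54%. None of these figures is an upper bound, since both r and k are assumed. The ratio hardly depends on sample size between 44 and 100 per arm. Confidence is medium because the SAP's wording is loose and the size of the gain cannot be fixed from the documents.

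**What to change.** State in the SAP that, for each continuous scale on which the targets are to be compared (for example MADRS and PHQ-9, listed in advance), the F3 versus 5.5cm comparison is an ANCOVA of the post-treatment score on randomised arm plus that scale's own baseline. Report the adjusted F3 minus 5.5cm difference with its 95% confidence interval, in place of the unadjusted between-arm t-test. Naming the two arms in that sentence also closes off the pre/post reading.

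Keep the pre/post summaries and the norm-referenced iPad comparison, without using them as evidence on target location. Keep the remission and response differences as planned.

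The cost is a change of SAP wording and one model per listed scale. No new data are needed, and because each model replaces a t-test one for one, no comparisons are added.

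### Pre-post t-tests and population norms cannot separate an rTMS effect on cognition from retest gain and natural course; the SAP should name the F3 minus 5.5 cm difference in change as the test

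*SAP*

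**What the plan says.** The Data Analysis Plan in the SAP opens with the contrast: "We will compare pre- and post-treatment rating scales, cognitive scores, and EEG/MRI results". It assigns t-tests to the cognitive and neurobehavioral scores, without saying whether they are paired or between arms, or one- or two-sided. For the tablet tests it names an external reference: "iPad cognitive testing is normed to a US population adult control and results will be analyzed as T-statistics comparing the patients against a general population". The next sentence promises a comparison of mean changes with confidence intervals, again without saying which groups are compared. For heart rate variability (HRV) only, data from IRB#201810778 serve as an outside comparison group.

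The protocol's Study Procedure Timeline lists the baseline assessments. They include the NIH Toolbox cognitive and emotional batteries, the MOCA and neurobehavioral testing. In a further task, "Patients will have heart rate variability and facial movements monitored while viewing video clips or images" or while hearing stories. The retest comes "After a patient has either completed their rTMS course or the course has been terminated by the rTMS team for whatever reason", and then "the patient will have the same testing performed as was performed at their initial study visit". The interval is therefore not fixed. Under the MRI heading, for roughly 25 patients, "a repeat neuroimaging or neurobehavioral assessment session may be completed partway through the TMS course".

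The same Timeline section randomises patients to F3 or 5.5 cm targeting. Both are active treatment. No sham, untreated or test-only group is described, and no alternate test form, practice-adjusted norm or reliable-change method.

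**The concern.** A patient who sits a cognitive battery a second time may score higher because the tasks are familiar. Patients also enter when they present for treatment of depression, so some improvement by the second visit can come from natural course and regression to the mean. With every patient on active rTMS, a pre-post change adds these components to any treatment effect, and nothing in a single-group contrast separates them. A population norm does not help: it shows where a patient stands relative to others, and as described it is not a norm for people tested twice.

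What is at stake is the meaning of a significant cognitive result. The design can show whether cognitive change differs between F3 and 5.5 cm, which is the trial's own question. It cannot show that rTMS changed cognition. The SAP does not say which of these its t-tests address.

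**Working it through.** **The plan's own figure.** The SAP gives no effect size, retest gain or power for cognition. Its one calculation is for remission (31% against 35%, 88 patients). That figure does not reproduce: a two-sided comparison needs 2169 per arm. This is a separate matter and the present point does not depend on it. I use 88 and 200 only as numbers of complete pairs.

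**Inputs.**
- From the SAP: alpha 0.05; N = 88 or 200.
- Assumed, because the documents give neither: retest gain g = 0.1, 0.2 or 0.3 baseline SD; retest correlation r = 0.6 to 0.8.
- Assumed: no rTMS effect, two-sided test, equal SD at both visits, complete pairs.

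**Step 1: what the norm does.** A norm-referenced score is a fixed rescaling, (x − μ)/σ, with population values μ and σ. In post minus pre, μ cancels and a gain of gσ remains as g. If the score has the usual SD of 10 (also assumed), g = 0.2 appears as a rise of 2 points. The norm removes none of it.

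**Step 2: the pre-post test.** In baseline SD units, the SD of change is √(2(1 − r)): 0.775 at r = 0.7 and 0.632 at r = 0.8. The standardised shift is dz = g/√(2(1 − r)). The rejection probability comes from the noncentral t with N − 1 degrees of freedom and noncentrality dz√N.

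For g = 0.2:
- r = 0.7: dz = 0.2/0.775 = 0.258. Noncentrality is 0.258 × √200 = 3.65, or 0.258 × √88 = 2.42. Rejection: 95% and 67%.
- r = 0.8: dz = 0.2/0.632 = 0.316. Noncentrality is 0.316 × √200 = 4.47, or 0.316 × √88 = 2.96. Rejection: 99% and 84%.

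Full range, with no rTMS effect:

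| Complete pairs | g | r = 0.6 | r = 0.7 | r = 0.8 |
|---|---|---|---|---|
| 88 | 0.1 | 18% | 22% | 31% |
| 88 | 0.2 | 55% | 67% | 84% |
| 88 | 0.3 | 88% | 95% | 99% |
| 200 | 0.1 | 35% | 44% | 61% |
| 200 | 0.2 | 88% | 95% | 99% |
| 200 | 0.3 | >99% | >99% | >99% |

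With g = 0 every cell is 5%.

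**Step 3: the between-arm test.** Let c be the shift from natural course and regression to the mean. Expected change is τ(F3) + g + c in one arm and τ(5.5) + g + c in the other. The difference is τ(F3) − τ(5.5), so the shared terms cancel. In simulation (r = 0.7, 4000 runs per setting, g = 0.1 to 0.3, N = 88 and 200) a t-test of change between arms rejected in 4.5–5.4% of trials. In the same data the pooled pre-post test rejected in 21–66–95% of trials at N = 88 and 45–96–100% at N = 200, for g = 0.1, 0.2 and 0.3 in turn.

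**The case against.** The strongest reply is that the SAP may already plan the right test. Directly after the norm sentence it promises a comparison of mean changes, and in a trial randomised between two targets and titled for target location this can naturally be read as F3 against 5.5 cm. A reader might infer that the SAP uses norms in place of the between-arm contrast. The text does not support that: it leaves the contrast unspecified. But it does state the pre-post comparison and the norm comparison, and nowhere ties the cognitive tests to the arms, so the ambiguity still needs resolving.

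Three other stronger readings also go too far.
- A reader might infer that the investigators will present cognitive change as an effect of rTMS. No passage says so. The point is that the stated analyses could not support such a claim.
- A reader might infer that the same clips or stories are shown twice, so that responses fade through habituation. Repeating the testing does not establish that identical material is reused, and the documents are silent.
- A reader might say that there is no outside comparison at all. HRV has one, but the SAP does not describe its population or say that it was tested twice, so it is not shown to control for retest effects.

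It is also fair to object that the rejection rates rest on assumed values, cover retest gain only, and take every recruited patient as a complete pair. They show how readily a large paired test picks up a small shift, not how large the shift is here.

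**Conclusion.** The point holds in limited form. The pre-post and norm-referenced comparisons of cognitive and neurobehavioral scores cannot separate treatment from retest gain, natural course and regression to the mean, and the SAP does not say that its t-tests or mean-change comparison are between targets. If they are run as pre-post tests, false-positive rates far above 5% are plausible: 35–61% at 200 pairs even for a 0.1 SD gain, with r from 0.6 to 0.8. These figures depend wholly on the assumed g and r; if there were no gain and no natural improvement, the test would hold its level.

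The randomised comparison is not biased by these effects, provided that retention, retest interval and the optional mid-course session are similar in the two arms. The trial's main question is therefore intact. The change is nonetheless worth making, because it replaces an uninterpretable test with one that the existing randomisation supports.

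**What to change.** In the Data Analysis Plan of the SAP:

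1. Make the F3 minus 5.5 cm difference in change the inferential test for the cognitive, emotional-battery and neurobehavioral outcomes, preferably adjusted for the baseline score, and state its sidedness.
2. Report within-arm pre-post change, and norm-referenced scores at either visit, descriptively with confidence intervals. State that they combine treatment, retest and natural-course effects.
3. Handle HRV change in the same way, since the IRB#201810778 group is not described as retested.

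This is a wording change, with no extra patients, visits or test material. It has two costs. The trial makes no inferential claim about rTMS itself on these outcomes. The unadjusted between-arm contrast is also less precise than the pooled pre-post change: at N = 200 and r = 0.7 its standard error is 0.775 × √(2/100) = 0.110 SD, against 0.775/√200 = 0.055 SD. Baseline adjustment would recover part of that.
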